## **6. STUDY POPULATION ANALYSES**

### **6.1. Overview of Planned Study Population Analyses**

The study population analyses will be based on the Safety analysis set.

Study population analyses including analyses of subject disposition, demographic and baseline characteristics, medical history, prior and concomitant medications.

Coefficients and Bayesian posterior probabilities for treatment differences is displayed for baseline characteristics.

Details of the planned displays are presented in **Error! Reference source not found.**

Categorical variables will be summarized by the number and percentage of subjects. Continuous parameters will be summarized by N, Range, Mean (minimum, maximum), Standard Error of mean (SE), Standard Deviation (SD) (for normally distributed data), or Median and interquartile range (IQR) for non-normally distributed data unless otherwise specified.

Disposition summary includes: subject screened, randomized and disposition at end of study – Day 28 along with reasons for withdrawals will be presented based on number of subjects and percentage. Subjects in different analysis populations will also be presented.

The screen failure reasons will be presented based on number of subjects and percentage. The percentage will be calculated based on total number of screened subjects.

Protocol Number: HBCOVID03  
Hope Biosciences  
Statistical Analysis Plan

Confidential

Date: 7-Nov-2022  
Version: 1.0  
Status: Draft

## 7. EFFICACY ANALYSES

### 7.1. Primary Efficacy Analyses

#### 7.1.1. Endpoint / Variables

The primary efficacy endpoints are changes from baseline in the following outcomes at each post-baseline visit:

- Inflammatory markers (TNF-alpha, IL-10, IL-6, C-Reactive protein)
- Oxygenation
- Time to return to room air (RTRA) and proportion of patients with room air status

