## 2.2. Study Design

Overview of Study Design and Key Features	
Randomized, double-blind, placebo-controlled, parallel group study	
Design Features	

• Randomized, double-blind, Placebo controlled study.

• 100 Subjects

• 2 Treatment groups

▪ Group 1 → HB- adMSCs

▪ Group 2 → Placebo

• Duration of treatment: up to 7 days, and overall study includes screening (up to 7 weeks prior to randomisation), and 4 treatment visits after randomisation scheduled at Infusion 1 (Day 0), Infusion 2 (Day 3), Infusion 3 (Day 7), and Infusion 4 (Day 10). Follow-up at day 28 (EOS).

Dosing	

• HB- adMSCs (Hope Biosciences adipose derived mesenchymal stem cells) is to be administered as an IV infusion with a dose of 100 million cells

• Placebo is to be administered as an IV infusion. Contains Saline solution 0.9%

Treatment Assignment	

• Participants will be randomised 3:2 to receive HB-adMSCs active treatment or Placebo.

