## **2.4. Statistical Hypotheses**

The null hypothesis is treatment with HB-adMSCs does not cause changes in primary and secondary endpoints (see outcomes) for suspected Corona Virus Disease. The alternative hypothesis for this study is that HB-adMSC treatment does result in changes from baseline values of primary and secondary endpoints in patients with suspected Corona Virus Disease. Hypotheses will primarily use Bayesian inference. (Any frequentist analyses performed as supplement will consider the hypothesis two-sided and tested at the 5% significance level.)

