## 5.3. Baseline Definitions

For all endpoints, the baseline value will be the latest pre-treatment assessment visit with a non-missing value. i.e., If an assessment has been made both at screening visit (Visit 1), and Day 0, infusion 1 visit (Visit 2, Day 0), the value from the Day 0 visit is used as the baseline value. If the value measured at the Day 0 visit is missing and the assessment also has been made at screening, then the screening value is used as the baseline value.

Unless otherwise stated, if baseline data is missing, no derivation will be performed and baseline will be set to “missing”.

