The Bayesian approach addresses these questions: (1) “Among patients with suspected COVID-19, what is the probability that allogeneic HB-adMSC 100mm confers benefit relative to placebo on status on inflammatory markers (C-Reactive protein, TNF-alpha, IL-6, IL-10), change from baseline oxygenation, and time to return to room air (RTRA) at treatment Day 10?” (2) “What is the best estimate of these effects?” and (3) “What is their precision?” By estimating the probability that such effects exist, we are assessing the probability that the alternative hypothesis is true; a probability that is, by definition, not accessible to Frequentist methods. The FDA has discussed the use of Bayesian statistical methods to make decisions regarding the efficacy of new treatments as an alternative to Frequentist methods in developing clinical applications. The current proposal will provide the optimal, unbiased estimates for the benefit conferred by allogeneic HB-adMSC, while also estimating the probability that such effects exist. Posterior distributions can then be used as informative priors for continued monitoring in expansions of treatments and treatment strategies exhibiting initial promise.

Presentation of results from the statistical models will include the estimated conditional/marginal mean treatment effects. For all endpoints analysed statistically, estimated mean treatment differences will be presented together with 95% credible intervals and posterior probabilities,

HB-adMSCs 100MM vs Placebo

All safety evaluations will be presented using Safety Analysis Set. The efficacy analysis will be presented using Efficacy analysis set.

Individual safety and efficacy parameters will be listed.

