#### **7.1.4.2. Data Analytic Models**

All primary endpoint efficacy measurements available at post-baseline at scheduled measurements (Visits 2 through 5 [infusions 1 through 4] for inflammatory markers, oxygenation, and room air status) will be analysed in a generalized linear mixed model. The model will predict each outcome as a function of the interaction between the fixed factors treatment group and time, controlling for lower order effects of time and treatment group. Models will control for stratification variables (see [Covariates and Other Strata](#)), and subject will be included as random effects.

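### SAP 5.7 asks the primary question at Day 10, SAP 7.1.1 makes every post-baseline visit primary, and nothing says which visit decides

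*SAP*

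**What the plan says.** Three places in the SAP bear on the timing of the primary result.

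- **Section 5.7 (General Considerations)** asks for the probability of benefit on the inflammatory markers, "change from baseline oxygenation, and time to return to room air (RTRA) at treatment Day 10".
- **Section 7.1.1** defines the endpoints by visit, without ranking the visits: "The primary efficacy endpoints are changes from baseline in the following outcomes at each post-baseline visit".
- **Section 7.1.4.2** fits one mixed model per outcome to "All primary endpoint efficacy measurements available at post-baseline at scheduled measurements (Visits 2 through 5 [infusions 1 through 4"]). It adds: "The model will predict each outcome as a function of the interaction between the fixed factors treatment group and time". It does not say which estimate from the model is the primary result.

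Section 2.2 gives the calendar: "Infusion 1 (Day 0), Infusion 2 (Day 3), Infusion 3 (Day 7), and Infusion 4 (Day 10"). Under section 5.3, when both screening and Day 0 values exist, "the value from the Day 0 visit is used as the baseline value".

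For reporting, section 5.7 says that "estimated mean treatment differences will be presented together with 95% credible intervals and posterior probabilities". No posterior-probability threshold for efficacy is given. The protocol lists the change-from-baseline endpoints in its synopsis, endpoint section and efficacy analysis, and names no visit in any of them.

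**The concern.** A Day 10 contrast and a contrast at every visit are different primary results, and they can disagree in the same data. If oxygenation separates at Day 3 and the arms have converged by Day 10, section 7.1.1 contains a favourable primary result and section 5.7 does not. The plan has no rule for that case.

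The rest of the SAP does not close the gap. Section 5.5 applies regularizing priors to secondary analyses. For confirmatory analyses it refers to error rates in a sample size justification section, which does not appear in the SAP text supplied for review. The primary models in section 7.1.4.1 use priors described as diffuse and neutral. By-visit cross-sectional analyses in section 7.2.4.1 are called exploratory and are shrunk, but they belong to the secondary methods. The by-visit primary contrasts thus have less protection than the secondary ones.

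**Working it through.** The plan states no error rate for the choice of visit, so there is no planned figure to reproduce. The check sizes what the open choice allows.

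**1. Candidate visits.** Visits 2 to 5 are Days 0, 3, 7 and 10 (SAP 2.2 and 7.1.4.2). Day 0 is the baseline (SAP 5.3). That leaves 4 − 1 = 3 post-baseline visits: Days 3, 7 and 10. The choice applies to the four markers and to oxygenation. The room-air proportion could also be read at each visit. Time to return to room air is a time-to-event outcome and has no change per visit.

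**2. Criterion.** The SAP gives no efficacy cut-off. Assume that benefit is claimed when its posterior probability exceeds 95%, and treat the prior as flat. The posterior probability of benefit is then Φ(z), and the criterion is z > 1.645. With no effect, one fixed visit meets it 5% of the time.

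**3. Independent visits (upper reference).** 1 − (1 − 0.05)³ = 1 − 0.857375 = 14.3%.

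**4. Correlated visits.** Repeated measures on the same patients are correlated. The documents give no correlation, so a range is assumed. With (Z₃, Z₇, Z₁₀) trivariate normal, mean 0, variance 1 and common correlation ρ, the quantity is P(max Z > 1.645). For the supplementary frequentist analyses ("Any frequentist analyses performed as supplement will consider the hypothesis two-sided and tested at the 5% significance level") it is P(max |Z| > 1.96). Results from 1,000,000 simulated draws:

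| ρ | Any of 3 visits, posterior > 95% | Any of 3 visits, two-sided 5% |
|---|---|---|
| 0.3 | 13.0% | 13.6% |
| 0.5 | 11.8% | 12.5% |
| 0.7 | 10.3% | 10.9% |
| 0.8 | 9.3% | 9.8% |
| One fixed visit | 5% | 5% |

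If correlation instead decays with visit spacing (first-order autoregressive, 0.5 / 0.7 / 0.8), the posterior > 95% column becomes 12.2 / 10.8 / 9.7%.

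**5. Ratio.** 10.3 / 5 = 2.1 and 13.0 / 5 = 2.6, so open choice of visit gives two to two and a half times the single-visit rate, per endpoint.

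**6. Is the Day 10 contrast defined by the model?** Only once the role of Day 0 is settled. Section 5.4.1 makes baseline a covariate, while section 7.1.4.2 counts Visit 2 among the post-baseline outcomes.

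- If Day 0 is an outcome and visit is categorical with Day 0 as reference, the treatment-by-Visit-5 term is (active Day 10 − active Day 0) − (placebo Day 10 − placebo Day 0). That is the difference in change from baseline.
- If Day 0 is a covariate and Day 3 is the reference visit, the Day 10 contrast is the treatment term plus the treatment-by-Visit-5 term.

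**The case against.** The strongest reply is that the sections do separate jobs: 5.7 states the question, 7.1.1 lists the repeated measurements and 7.1.4.2 gives the model. On that reading the defect is one unranked contrast. This is a fair description, but the gap remains, because 7.1.1 gives primary status to every visit and no text withdraws it.

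The Day 10 phrase in 5.7 could also be read as attached only to time to room air, the last item in its list. The markers and oxygenation would then have no decisive visit anywhere, which leaves the same gap.

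A Bayesian analysis without a threshold has no formal error rate, and treatment differences are to be shown for all endpoints, so a favourable visit would probably appear beside the others. Both points stand, and they make the percentages illustrative. Display still does not say which visit answers the primary question when visits disagree.

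Four stronger readings are tempting, and the documents do not support them:

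- *The sponsor means to pick the best visit.* Nothing shows intent.
- *The treatment-by-time interaction is a third stated primary quantity.* Section 7.1.4.2 specifies a model and does not name the interaction as primary.
- *An effect reached by Day 3 and held to Day 10 would be invisible in the interaction.* With Day 0 kept as an outcome and visit categorical, it appears in the treatment-by-visit terms. The claim holds only if Day 0 is dropped as an outcome.
- *The trial-wide chance of a spurious primary finding is 48-56%, against 1 − 0.95⁶ = 26% at Day 10 only.* This needs six independent endpoints. With assumed between-endpoint correlation of 0.3-0.5 the figures are about 33-48% and 18-22%. The Day 10 part is multiplicity across endpoints, which is a different problem.

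**Conclusion.** The inconsistency between SAP 5.7 and 7.1.1 is real, and neither document resolves it. Days 3, 7 and 10 can each supply the primary result for each marker and for oxygenation. Under no effect, the chance that at least one visit supports benefit is about 10-13% per endpoint, against 5% for one fixed visit. This rests on three assumptions that are not in the plan: a 95% posterior cut-off, a prior that is effectively flat, and between-visit correlation of 0.7 to 0.3. The inconsistency itself depends on none of them. It should be corrected. It shows latitude in the text and is not evidence of selective reporting.

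**What to change.** Replace the endpoint definition in SAP 7.1.1 with:

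> The primary estimate for each inflammatory marker and for oxygenation is the HB-adMSC minus placebo difference in change from baseline at Visit 5 (Day 10), from the model in 7.1.4.2 with visit as a categorical factor; the contrasts at Days 3 and 7 are supportive. For room air, the primary endpoint is time to return to room air, as in the protocol; the proportion on room air at each visit is supportive.

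The room-air sentence is needed because the SAP places the proportion among the primary endpoints, while the protocol's primary list has only the time to return to room air.

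In 7.1.4.2, state whether Day 0 is an outcome or a covariate, so that the Day 10 contrast is defined. The supportive label should apply to the Day 3 and Day 7 contrasts and not to the interaction as a whole, because under one coding the interaction term at Visit 5 is the Day 10 contrast.

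The cost is a few sentences in a SAP that is dated 7-Nov-2022 and still marked as a draft. The downside is that an effect seen only at Day 3 or Day 7 cannot be called primary. If unblinded results have already been examined, the choice of visit should be reported as post hoc. The change sets no efficacy threshold and does not deal with the number of primary endpoints; both need separate attention.

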#### 7.1.2. Summary Measure

Mean values (descriptive, unadjusted for covariates) and conditional means from the Bayesian generalized linear (mixed) models (estimated, adjusted for covariates) will be provided for each endpoint.

#### 7.1.3. Population of Interest

The primary efficacy analyses will be based on the efficacy analysis set population, unless otherwise specified.

#### 7.1.4. Statistical Analyses / Methods

Details of the planned displays are provided in **Error! Reference source not found..**

#### **7.1.4.1. Statistical Methodology Specification**

Initial analyses examining group differences for baseline variables will use cross-tabulation, ANOVAs, and examination of correlations between baseline variables and specified outcomes. For the purposes of evaluating the comparability of groups, a posterior probability of  $\geq 75\%$  will constitute evidence for statistically reliable differences. Baseline or demographic variables on which group differences are detected, and which are correlated with outcomes, meet the definition of confounders and will result in two sets of analyses: one in which only the stratification variables are included as covariates, and another where the relevant variable is included as a covariate. This will permit determination of the degree to which any group differences might confound conclusions regarding treatment. A third set of analyses will model the effect of treatment group (controlling for stratification variables) on each outcome, focusing on the subgroup of patients who survived through the last infusion visit where statistically feasible.

Broadly, the data analytic strategy will use generalized linear, multilevel, and survival/cox proportional hazard models (R v 4.1, 2021; brms v 2.17; RStan v 2.21) for discrete, continuous, and time-to-event outcomes. Multilevel generalized linear modeling to account for clustering of patients within site and repeated observations within patients will evaluate continuous, dichotomous, and count data. All analyses will address potential missingness through joint modeling of observed outcomes and the missing data, an approach robust to ignorable missingness (i.e., MCAR and MAR). Sensitivity analyses will evaluate robustness of analytic conclusions to missing data. Non-ignorable missing data patterns will be addressed through pattern-mixture modeling methods.

Evaluation of posterior distributions will permit statements regarding the probability that effects of varying magnitudes exist, given the data. Specification of diffuse, neutral priors will reflect the initial uncertainty regarding effect sizes. For all generalized linear models, priors for regression coefficients will be specified as  $\sim$ Normal ( $\mu=0$ ,  $\sigma^2=1 \times 10$ ), and priors for the levels one and two error variances will be specified as  $\sim$ Half-Normal ( $\mu=0$ ,  $\sigma^2=1 \times 10^3$ ). The choice of prior distribution for level two variances will follow Gelman's recommendations from the literature. Priors for the comparison of proportions will be specified as  $\sim$ Beta ( $\alpha=1.0$ ,  $\beta=1.0$ ).

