## 5. CONSIDERATIONS FOR DATA ANALYSES AND DATA HANDLING CONVENTIONS

### 5.1. Treatment Group Comparability

Initial analyses examining group differences for baseline variables will use cross-tabulation, ANOVAs, and examination of correlations between baseline variables and specified outcomes. For the purposes of evaluating the comparability of groups, a posterior probability of > 95% will constitute evidence for statistically reliable differences. Baseline or demographic variables on which group differences are detected (excluding stratification variables), and which are correlated with outcomes, meet the definition of confounders, and will result in two sets of analyses: one in which the relevant variable is included as a covariate, and one in which it is not. This will permit determination of the degree to which any group differences might confound conclusions regarding treatment.

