## **5.4. Examination of Covariates, Other Strata and Subgroups**

### **5.4.1. Covariates and Other Strata**

Baseline will be included as a covariate in the efficacy analyses, wherever applicable. Stratification variables used at randomization (site, illness severity, pre-existing condition, ethnicity, age group) will be included as covariates.

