### 7.2.4.1. Statistical Methodology Specification

Principles will follow the same procedures as the Primary Efficacy analyses (see 7.1.4.1). Three sets of analyses will be performed: the first adjusting for stratification variables, a second set adjusting for variables found to be confounding (see 7.1.4.1), and a third set focusing on the subgroup of surviving patients as of the last infusion where statistically feasible. Bayesian generalized multilevel models will evaluate the differential trajectories of each secondary endpoint as a function of treatment, time, and the interaction of treatment and time.

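### SAP 5.4.1 makes the baseline value a covariate, but the section 7 model statements name only the stratification variables and keep Day 0 as a response, so marker and oxygenation changes can be analysed unadjusted for baseline, at a cost in precision

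*SAP*

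**What the plan says.** The SAP gives its covariate rule in several places.

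- **5.4.1** has two separate sentences. The first is "Baseline will be included as a covariate in the efficacy analyses, wherever applicable". The second is "Stratification variables used at randomization (site, illness severity, pre-existing condition, ethnicity, age group) will be included as covariates". The outcome's own baseline value is not one of the five variables in that list.
- **7.1.4.1** covers the case where a confounder is found. The two resulting sets are "one in which only the stratification variables are included as covariates, and another where the relevant variable is included as a covariate". The trigger is: "Baseline or demographic variables on which group differences are detected, and which are correlated with outcomes, meet the definition of confounders". A third set restricts to patients alive at the last infusion visit and again controls for the stratification variables.
- **7.1.4.2** specifies treatment, time and their interaction, the stratification variables (with a link to 5.4.1) and a random subject effect. It lists Visits 2 to 5 as the post-baseline measurements. Visit 2 is the Day 0 visit, which 5.3 defines as the usual source of baseline.
- **7.2.4.1** describes the secondary sets as "the first adjusting for stratification variables, a second set adjusting for variables found to be confounding", with a third in survivors. **7.2.4.2** repeats the model of 7.1.4.2, with the same link and again starting at Visit 2.

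On the outcome itself, 7.1.1 says: "The primary efficacy endpoints are changes from baseline in the following outcomes at each post-baseline visit".

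**The concern.** Section 7 is what a programmer will work from, and none of its model statements names the baseline value. Taken at its word, 7.1.4.1 describes a set that leaves out a covariate which 5.4.1 puts in. A marker's Day 0 value could then enter only through the confounder route, which depends on the observed imbalance.

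The outcomes affected are TNF-alpha, IL-10, IL-6, CRP and oxygenation, all defined as change from baseline. For such an outcome, a change score without the baseline value is less precise than the same analysis with it, and the data are already in hand. The protocol set the sample size by expected demand, not by an effect size, so there is no stated margin to absorb the loss. Because the confounder route is applied variable by variable, the five outcomes could also end up adjusted differently from one another by chance.

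**Working it through.** The documents state no power, effect size, SD or baseline-to-follow-up correlation, so there is no design figure to reproduce.

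**Inputs.** 100 patients at 3:2, so 60:40 (protocol, Investigational Plan; SAP 2.2). 15% drop-out (protocol synopsis) leaves 51:34 if it is equal in both arms. Assumed: correlation r between baseline and follow-up, equal variances at each visit, no other prognostic covariate.

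**Step 1. Single-visit comparison.** In units of the outcome variance, the change score has variance 2(1 − r) and the baseline-adjusted analysis 1 − r². The information lost is 1 − (1 − r²)/[2(1 − r)] = (1 − r)/2. Ignoring the prior, intervals widen by the factor √[2/(1 + r)].

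| r | 2(1 − r) | 1 − r² | Loss | Interval width ratio |
|---|---|---|---|---|
| 0.2 | 1.60 | 0.96 | 40% | 1.29 |
| 0.5 | 1.00 | 0.75 | 25% | 1.15 |
| 0.7 | 0.60 | 0.51 | 15% | 1.08 |

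**Step 2. The model in 7.1.4.2.** Take Days 0, 3, 7 and 10 as responses, a random intercept, categorical time by treatment, and 51:34. With baseline means free, the Day 0 to Day 10 contrast has variance 2(1 − r)(1/51 + 1/34), where 1/51 + 1/34 = 0.0490. By generalised least squares:

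- r = 0.2: 0.0784 with baseline means free, 0.0471 with them constrained equal;
- r = 0.5: 0.0490 and 0.0368;
- r = 0.7: 0.0294 and 0.0250.

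The free-means figures are the change-score variances and the constrained figures the baseline-adjusted ones, so the losses in the table carry over. With linear time the losses are 46%, 26% and 14%. For the average of the three later visits the loss is 3(1 − r)/4, or 60%, 37.5% and 22.5%.

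**Step 3. Does adding the covariate alone help?** With Visit 2 in the response, the contrast is a within-patient difference, and a covariate that is constant over time cancels out of it. Simulated complete data of this shape (r = 0.3, 0.5, 0.7) gave identical interaction estimates with and without the covariate, and standard errors within 0.0005. With changes at Visits 3 to 5 as the response, adding baseline altered the Day 10 estimate and, at r = 0.5, cut its standard error from 0.224 to 0.195. Theory gives √0.0490 = 0.221 and √0.0368 = 0.192.

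**Step 4. Is chance imbalance a second harm?** No. The excess variance is 2(1 − r) − (1 − r²) = (1 − r)², which is exactly the variance contributed by (1 − r) times the baseline difference. The two are one quantity.

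**Step 5. The confounder route.** A posterior probability of at least 75% in 7.1.4.1 "will constitute evidence for statistically reliable differences"; 5.1 uses more than 95% for the same purpose. Assuming near-flat priors, no true difference and flagging in either direction, a baseline would meet the imbalance test in about 50% of trials under the first rule and 10% under the second. At 51:34 the 75% rule corresponds to a difference of about 0.674 × 0.221 = 0.15 SD. The variable must also correlate with outcome.

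**The case against.** A reading that keeps the baseline value is available. Sections 7.1.4.2 and 7.2.4.2 link to 5.4.1, which contains the baseline sentence. The parallel text in 5.1 contrasts "one in which the relevant variable is included as a covariate, and one in which it is not", without the word only, so 7.1.4.1 may simply mean without the extra confounder. This softens the conflict but does not resolve it: the link is offered as the source of the stratification variables, and the restrictive word stands in the primary methods section.

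A reader might infer that the SAP makes the unadjusted set its lead analysis. It does not: no section ranks the sets as primary, 7.2.4.1 merely lists one first, and in 7.1.4.1 the pair arises only when a confounder is found. A reader might also take 5.4.1 as a flat requirement, but it carries a qualifier on applicability. That qualifier hardly exempts a continuous change-from-baseline outcome.

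Nor do the two sections necessarily yield different estimates. In the 7.1.4.2 model with Visit 2 as a response and complete data, the change contrast is the same with or without the covariate. They differ when the response is the change at Visits 3 to 5, which is the outcome as 7.1.1 defines it.

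Finally, the confounder set would pick up some of the larger imbalances and be reported alongside. That is partial and data-dependent protection, and its two thresholds disagree.

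**Conclusion.** The inconsistency is real and should be corrected. Section 7 read literally drops a covariate that 5.4.1 includes, and the Visit 2 wording makes the marker and oxygenation effect a change-score contrast in any case.

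The consequence is lost precision. Under randomisation the omission does not bias the estimate on average, and a chance baseline difference carried into the result is that same loss, not an additional one. The 15% to 40% range is not a property of this trial. It follows from an assumed r between 0.7 and 0.2, equal variances, one follow-up visit and no other prognostic covariate. Adjustment for illness severity may recover part, and the formula does not extend to room-air status or time to room air. No loss from a stated design power can be quoted, since none is given and inference is primarily Bayesian.

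**What to change.** Two changes are needed together.

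1. In 7.1.4.1, 7.1.4.2, 7.2.4.1 and 7.2.4.2, state that every efficacy model for an outcome with a baseline value includes that value plus the stratification variables, in all three sets. The confounder set then adds variables to that model.
2. In the repeated-measures models, take Visit 2 out of the response (leaving Visits 3 to 5 for markers and oxygenation, and correspondingly for the secondary outcomes). Alternatively, keep Visit 2 as a response with baseline means constrained equal between arms; that constraint then does the work of the covariate.

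The first change without the second leaves the change contrast as it is. The second without the first is also not enough: raw follow-up values modelled with no baseline term lose r² of the information (4%, 25% and 49% at r = 0.2, 0.5 and 0.7). It would also help to name which set is primary.

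The cost is SAP wording, in a document still marked as a draft, and one coefficient per model from data already collected.
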